5.4. PER PROTOCOL SET

The per protocol set (PPS) will include all patients in the full analysis set who have no major protocol violations to be determined at the Blinded Data Review Meeting (BDRM). Patients will be analyzed according to randomized treatment. The PPS will be used for all analyses of primary and secondary efficacy endpoints.

5.5. PROTOCOL DEVIATIONS AND VIOLATIONS

A protocol deviation is any change or alteration from the procedures stated in the study protocol, consent document, recruitment process, or study materials (e.g., questionnaires).

A major protocol violation is a deviation that has an impact on subject safety, may

substantially alter risks to subjects, may have an effect on the integrity of the study data, or may affect the subject's willingness to participate in the study. Major protocol violations include (but are not limited to): deviation from inclusion/exclusion criteria, withdrawal criteria met during the study but subject was not withdrawn, prohibited concomitant medications, substantial deviations from the dosing schedule.

A minor protocol violation is a deviation that does not impact subject safety, compromise the integrity of the study data, or affect the subject's willingness to participate in the study.

Protocol deviations will be documented during the study period using the IMPACT monitoring database and will be assigned into one of the following categories:

- Visit schedule;
- Concomitant medication;
- Dosing;
- Laboratory;
- Non-compliance;
- Visit/procedures requirements;
- Other.

This data will be exported from IMPACT and a listing will be generated with the date of occurrence, the category (as above), type of violation, and the reason for the deviation. The listing will be reviewed prior to database lock.

All protocol deviation/violation data will be listed and summarized on the safety analysis set.

6. GENERAL ASPECTS FOR STATISTICAL ANALYSIS

6.1. GENERAL METHODS

This section describes analytical analysis issues that relate to all or some of the analytic analysis sections that follow. It describes general guidelines for analysis as well as the following items:

- SAS version 9.4 or higher will be used.
- INC Research will be responsible for reporting the demographic, safety, and efficacy data including listings of the administration information for collection of samples.
- Unless otherwise specified, summaries will be presented for each treatment group and dose level and overall.
- The total number of patients in the treatment group and dose level will be used as the denominator for percentage calculations, unless stated otherwise in the table shell.
- Continuous variables will be summarized using the number of observations (n), mean, standard deviation (SD), median, 25th and 75th percentile, 5th percentile and 95th percentile, minimum, and maximum. Categorical variables will be summarized using number of observations (n), frequency and percentages of patients.
- All safety data will be entered in to the patient data listings. All patients entered into the database, including screen failures, will be included in the disposition listings. Patients who are screened only (who have given signed written informed consent) will be presented as a separate group at the end of the appropriate listings.
- All patients who provide informed consent will be accounted for in this study.
- In general, the listings will be sorted by dose level (treatment group), patient number, and assessment date (and time) if applicable.
- The summary tables will include the total column and columns as follows:
 - Placebo, 5 mg piromelatine, 20 mg piromelatine, 50 mg piromelatine.
- Multiple assessments at a given time point (planned, repeat, and unscheduled) will not be included in summary tables unless specified otherwise, but will be included in the listings. For example if there are multiple laboratory results at a given visit/time point, the latest non-missing value within the visit/time point window will be used. See the specific sections of the SAP for further descriptions.
- See [Section 12](#) for INC standard programming conventions.

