6.2. KEY DEFINITIONS

For the purposes of this study, the term “study drug” refers to piromelatine or placebo.

The study day is the day relative to the date of first dose of study drug, where day -1 is the day before the first dose of study drug and day 1 is the day of first dose of study drug (Week 0 (Visit 2)).

The last dose date is defined as the last non-missing date where a nonzero dose of study drug was recorded.

Unless otherwise specified, baseline is the last non-missing observation before the start of the study treatment, which is expected to be the baseline visit at Week 0, or Screening (if existing) if the Week 0 data are not available.

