9.4. LABORATORY EVALUATIONS

All blood and urine samples will be analyzed using a local laboratory. The sampling will be performed at the site at Screening (Visit 1), Visit 4 (Week 13), and Visit 5 (Week 26) and as soon as possible following the premature discontinuation visit (if applicable).

The following parameters will be measured:

- Hematology: hemoglobin, hematocrit, red blood cells, mean corpuscular hemoglobin (MCH), mean corpuscular volume (MCV), mean corpuscular hemoglobin concentration, large unstained cells, white blood cells, lymphocytes, monocytes, neutrophils, eosinophils, basophils and platelets.
- Chemistry: creatinine, uric acid, urea, aspartate aminotransferase (ASAT), alanine aminotransferase (ALAT), albumin, gamma-glutamyltransferase (GGT),

total protein, sodium, potassium, chloride, calcium, phosphorus, glucose, alkaline phosphatase, total bilirubin, total testosterone, free testosterone, Sex Hormone Binding Globulin (SHBG) and prolactin.

- Urinalysis: bilirubin, blood, clarity, color, glucose, ketones, leukocyte esterase, nitrite, pH, protein, specific gravity and urobilinogen.

All summaries of hematology, chemistry and urinalysis will be based on results in standard international (SI) system of units, conversion will be performed according to the data management plan (DMP) prior to the transfer to INC Research. The high and low classifications will be derived relative to the result and normal range in SI units.

Summary tables for hematology, chemistry and urinalysis laboratory variables will include the following: descriptive statistics for SI values and change from baseline for all continuous variables by assessment for each module and dose level. In general, any quantitative assessments for urinalysis will be summarized using the number and percentage of subjects with the given result. Percentages will be calculated out of the number of subjects with non-missing data. Shift tables showing the number of patients having values below, within and above the normal range at each assessment at Screening and each post baseline visit will be presented.

All laboratory results in original and SI units will be included in data listings. Tests will be listed in alphabetical order. Urine drug screen will be listed.

Optional blood sampling for ApoE4 genotyping (e4/e4, e4/e3, e4/e2, e3/e3, e3/e2, e2/e2) will be listed. This data will be collected and reported after DBL.

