Table 14.3.1.6	Treatment Emergent Adverse Events (TEAEs) Leading to Withdrawal of Study Medication by System Organ Class and Preferred Term	Safety Analysis Set
Table 14.3.1.7	Treatment Emergent Adverse Events (TEAEs) by Preferred Term	Safety Analysis Set
Table 14.3.1.8	All Adverse Events (AEs) by System Organ Class and Preferred Term	Safety Analysis Set
Table 14.3.1.9	All Adverse Events (AEs) by System Organ Class, Preferred Term and Maximum Severity	Safety Analysis Set
Table 14.3.2.1	Listing of all Serious Adverse Events Leading to Withdrawal from the Study	Safety Analysis Set
Table 14.3.4.1.1.1	Laboratory Results by Visit: Hematology	Safety Analysis Set
Table	Shift from Baseline in Laboratory Results by Visit:	Safety Analysis Set

14.3.4.1.1.2	Hematology	
Table 14.3.4.1.2.1	Laboratory Results by Visit: Chemistry	Safety Analysis Set
Table 14.3.4.1.2.2	Shift from Baseline in Laboratory Results by Visit: Chemistry	Safety Analysis Set
Table 14.3.4.1.3.1	Laboratory Results by Visit: Urinalysis	Safety Analysis Set
Table 14.3.4.1.3.2	Shift from Baseline in Laboratory Results by Visit: Urinalysis	Safety Analysis Set
Table 14.3.4.2	Vital Signs by Visit	Safety Analysis Set
Table 14.3.4.3.1	ECG Interval Results by Visit	Safety Analysis Set
Table 14.3.4.3.2	Overall Results of 12-lead ECG by Visit	Safety Analysis Set
Table 14.3.4.4	Overall Results of Physical Examination by Visit	Safety Analysis Set
Table 14.3.4.5.1	Total Sheehan-STS Results by Visit	Safety Analysis Set
Table 14.3.4.5.2	Individual Sheehan-STS Results by Visit	Safety Analysis Set
Table 14.3.4.6	Extent of Exposure	Safety Analysis Set

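### Laboratory tables keep only the latest value in each visit window and no worst post-baseline shift is planned, so by-arm counts of out-of-range results can be understated

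*SAP*

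**What the plan says.** SAP Section 6.1 deals with several results at one time point. It opens with "Multiple assessments at a given time point (planned, repeat, and unscheduled) will not be included in summary tables unless specified otherwise", sends all of them to the listings, and then takes laboratory data as its own example: "the latest non-missing value within the visit/time point window will be used". It leaves room for exceptions: "See the specific sections of the SAP for further descriptions".

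Section 9.4 is the specific section for laboratory data. It schedules samples at Screening, Week 13 and Week 26, and after premature discontinuation. It plans descriptive statistics, change from baseline and "Shift tables showing the number of patients having values below, within and above the normal range at each assessment at Screening" and each later visit. It has no rule for repeats and no worst-value summary. The index in Section 14 holds two tables per panel (hematology, chemistry, urinalysis): results by visit, and a shift table such as "Shift from Baseline in Laboratory Results by Visit: Chemistry".

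On the other side of the shift, Section 6.2 sets the default that "baseline is the last non-missing observation before the start of the study treatment".

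**The concern.** The shift tables are the only planned laboratory tables that count patients outside the normal range by arm. If a retest in the window replaces the value it was meant to check, a transient abnormality leaves those tables. Completers have two scheduled post-baseline laboratory visits, so one replacement can remove a patient's only out-of-range result.

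This trial is described as a dose-ranging safety and efficacy study, and its chemistry panel includes transaminases, prolactin and testosterone. For such tests a reader of the report will want to know how many patients in each arm were ever out of range on treatment. The by-visit tables do not answer that question.

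**Working it through.** The plan states no figure on this point, so there is none to reproduce. The check has two parts.

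**1. Following the rule through the document**

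- Section 6.1 selects the latest value in the window, with laboratory results as the named case.
- Section 6.1 allows a specific section to differ. Section 9.4 does not. Its reference to each assessment might be read as every sample, but the indexed tables are by visit, so this is too weak to count as an exception.
- Section 14 lists no worst post-baseline, maximum-shift, graded or marked-abnormality laboratory table.

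Take a patient who is out of range at the scheduled Week 13 sample and in range at a retest inside the Week 13 window. The shift table counts this patient as within range at Week 13. The retest also supplies the value for the mean and the change from baseline. The out-of-range value is only listed. A retest outside the window replaces nothing.

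**2. Size under stated assumptions**

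Let n be the arm size, p the share of patients out of range at the scheduled sample, r the share of those retested inside the window, and q the share of retests back in range. Then:

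- patients truly out of range at the scheduled sample = n × p
- patients shown out of range = n × p × (1 − r × q)
- share lost = r × q

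The SAP gives none of p, r and q; all three are assumptions. For n, the illustration uses the arm sizes in Section 3.6: 95 per active arm and 115 on placebo.

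With p = 5%:

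| r | q | Share lost | Shown, n = 95 (true 4.75) | Shown, n = 115 (true 5.75) |
|---|---|---|---|---|
| 0.25 | 0.25 | 6% | 4.45 | 5.39 |
| 0.5 | 0.5 | 25% | 3.56 | 4.31 |
| 1.0 | 0.5 | 50% | 2.38 | 2.88 |
| 1.0 | 0.8 | 80% | 0.95 | 1.15 |

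Middle case: 4.75 × (1 − 0.5 × 0.5) = 3.56 and 5.75 × 0.75 = 4.31.

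**Effect on a comparison of arms.** If r and q are equal across arms, rates shrink in proportion. With true rates of 10% and 5% and r = q = 0.5, the table shows 7.5% and 3.75%. The ratio stays at 2, and the difference falls from 5 to 3.75 percentage points. If abnormalities in an active arm were more often transient, the ratio would move as well. With r = 0.5, q = 0.8 on active and q = 0.25 on placebo, the table shows 10% × 0.6 = 6% against 5% × 0.875 = 4.4%, a ratio of about 1.4.

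**The case against.** Several points on the other side stand.

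- **The bullet in Section 6.1 does not contradict itself.** A reader might infer that its first sentence excludes repeat and unscheduled results while the example then selects the repeat. But planned assessments are in the same list, so read as an exclusion it would leave nothing to tabulate. The sensible reading is that not all values are tabulated, and the example says which one is kept.
- **The latest value is a defensible convention.** The SAP does not say why samples are repeated. If the first sample was doubtful or unusable, the later value is the better one. A reader might infer that by-visit tables should switch to the first or scheduled value; the document gives no basis for calling that choice right and the present one wrong.
- **The direction is not uniform.** A later out-of-range retest would replace an earlier normal value. The baseline default also takes the last pre-treatment value, so an abnormal Screening result followed by a normal retest gives a normal baseline, and a later abnormality then counts as a new shift. A net bias towards normal needs the assumption that retests mostly follow abnormal results. That is plausible but not in the SAP.
- **The dose comparison is not shown to be biased.** The rule is prespecified and the same in all arms, laboratory summaries are descriptive, and equal retest behaviour shrinks all arms alike. The unequal case above is an illustration only.
- **Nothing is deleted.** Every result is listed, and an abnormality reported as an adverse event reaches those tables. The table shells are not shown, so row content beyond the index titles cannot be checked.

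None of this supplies a by-arm count of patients who were out of range at any time on treatment. Listings do not give it, and adverse event tables depend on what was reported.

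**Conclusion.** The point holds as a limited gap in safety reporting. Applied as written, the latest-value rule can drop on-treatment abnormalities from the only by-arm tables of out-of-range laboratory results, and no planned table recovers them.

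The size is not determinable from the SAP. The loss is r × q: 25% if half of the out-of-range results are retested in the window and half of those are back in range, and 6% to 80% over the assumed ranges r = 0.25 to 1.0 and q = 0.25 to 0.8. A reader might infer that a large share is certainly lost. That would need nearly every abnormal result to be retested inside a window whose limits this document does not state.

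No efficacy conclusion depends on this point. It is an inexpensive improvement rather than the correction of an error.

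**What to change.** Keep the by-visit selection rule in Section 6.1. In Section 9.4, add to each hematology and chemistry shift table, and to urinalysis where a normal range applies, a row from baseline to the worst post-baseline on-treatment value. Build it from all scheduled, repeat and unscheduled results. Show the lowest and the highest value separately for tests where both directions matter. State in a footnote which results count as on-treatment, and adjust the index titles in Section 14.

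The cost is one row or panel per shift table and some programming on data already collected and listed. Abnormal counts will be higher in all arms than in the by-visit rows, and a doubtful first sample will be counted unless it has been marked invalid. A footnote should say that the two sets of rows answer different questions.

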6.2. KEY DEFINITIONS

For the purposes of this study, the term “study drug” refers to piromelatine or placebo.

The study day is the day relative to the date of first dose of study drug, where day -1 is the day before the first dose of study drug and day 1 is the day of first dose of study drug (Week 0 (Visit 2)).

The last dose date is defined as the last non-missing date where a nonzero dose of study drug was recorded.

Unless otherwise specified, baseline is the last non-missing observation before the start of the study treatment, which is expected to be the baseline visit at Week 0, or Screening (if existing) if the Week 0 data are not available.

6.3. MISSING DATA

In cases of missing baseline data for cNTB tests, the pre-baseline value will be taken for analysis. If the pre-baseline value is missing as well, values from Screening will be taken and used for analysis as baseline. In cases where the baseline value for COWAT, CFT and ADAS-cog14 are missing, values obtained at Screening will be taken and used for analysis.

Pattern mixture model imputation will be used to treat missing data for all analyses of covariance (ANCOVA) as described in [Section 8.1](#). In the case of cNTB composite scores the imputation will be carried out at the level of the composite score, not at the level of individual tests.

Missing data for AEs where toxicity and relationship to study drug are missing will be treated as described in [Section 9.3](#).

Missing or partial dates for concomitant medications and adverse events will be treated as described in Sections [7.6](#) and [9.3](#) respectively.

No other imputation of missing data shall be performed.

6.4. POOLING OF CENTERS

For all mixed-effects maximum likelihood repeated measures (MMRM) and ANCOVA models for the efficacy endpoints, data collected from investigators who enrolled fewer than 3 patients in any 1 treatment group will be combined prior to analysis. If this combination still results in a treatment group having fewer than 3 patients in any 1 treatment group, then this group of patients will be combined with the next fewest-enrolling investigator. In the event that there is a tie for fewest-enrolling investigator, one of these will be chosen at random by a random-number generator.

6.5. STATISTICAL ASSUMPTIONS

The inherent assumption of normally distributed data will be evaluated by generating output for the residuals from the full MMRM and ANCOVA models, which include the interaction term, and by testing for normality using the Shapiro-Wilk test. In the event that the data are predominantly non-normally distributed, analyses will also be conducted on the ranked data. This rank transformation will be applied by ranking all the data for a particular variable, across all investigators and treatments, from lowest to highest. Integer ranks will be assigned starting at 1; mean ranks will be assigned when ties occur.

6.6. SUBGROUPS

For the piromelatine treatment, the 20 mg and 50 mg arms will be combined to create an active arm subgroup. The active subgroup versus placebo analyses will be applied to all primary and secondary endpoints for the FAS using the MMRM.

Additional subgroups will be determined according to ApoE4 carrier status (the presence of ApoE4 allele), baseline insomnia severity (patients being below or above the PSQI cutoff score of ≥ 5) and naïve patients and those taking AD medication (acetylcholinesterase inhibitors and/or memantine) at baseline. These evaluations will be applied to all primary and secondary efficacy endpoints for the FAS using the MMRM model and will include also the calculation of effect size (Cohen's d).

7. DEMOGRAPHIC, OTHER BASELINE CHARACTERISTICS AND MEDICATION

7.1. SUBJECT DISPOSITION AND WITHDRAWALS

All patients who provide informed consent will be accounted for in this study.

The overall number of screened patients who have given written informed consent will be summarized for the screened set.

Patient disposition will be summarized for the screened set.

The study discontinuation along with the reasons for discontinuation as recorded on the eCRF, and the study day of discontinuation will be listed.

The study disposition summary tables will include the number and percentage of patients in each of the analysis sets and the reason for study discontinuation. Patients who are screen failures will be included in the all patients column. Flowcharts, similar to CONSORT study diagrams, will be created for each analysis set.

Subject disposition data will be listed on the screened set.

7.2. PROTOCOL DEVIATIONS AND VIOLATIONS

Protocol deviations will be captured by the clinical monitoring team on an ongoing basis throughout the study. These deviations will be discussed in a case-by-case process and classified into major and minor violations before the data base lock at the BDRM.

All protocol deviations will be summarized by major/minor violations (defined within the BDRM) and classification for each treatment group for the safety analysis set.

All protocol deviation/violation data will be listed on the safety analysis set.

7.3. DEMOGRAPHIC AND OTHER BASELINE CHARACTERISTICS

Age (years) will be calculated as the number of years between the date of birth and the date informed consent was recorded on the eCRF.

Age at Screening = (informed consent date - date of birth + 1) / 365.25 and truncated to complete years.

Age (years) and body mass index (BMI) will be summarized using summary statistics for continuous variables. Demography (sex, race, ethnicity, age, and child-bearing potential) will be summarized by treatment group for patients in the full analysis set.

Sex, race, ethnicity and child bearing potential will be summarized using the summary statistics for categorical variables.

Education status will be summarized using summary statistics for years of education achieved. Highest level of education achieved will be summarized using the summary statistics for categorical variables. Education status will be summarized by treatment group for patients in the full analysis set.

All demography and education status data will be listed on the safety analysis set.

7.4. MEDICAL/SURGICAL HISTORY

Medical/surgical history as recorded at Screening (Visit 1) will be summarized using the full analysis set by treatment group using the number and percentage of patients reporting each system organ class (SOC) and preferred term (PT). Medical/surgical history will be sorted by descending overall total by SOC and PT using the Medical Dictionary for Regulatory Activities (MedDRA) coding dictionary version 17.1 or later in the summary table.

Medical/surgical history data will be listed on the safety analysis set and sorted by treatment group, patient number, onset date, SOC, and PT.

7.5. OTHER BASELINE CHARACTERISTICS

Duration of AD and severity of insomnia as expressed by PSQI score at baseline will be summarized by treatment group using the full analysis set.

Duration of AD will be calculated as:

$(\text{Date of informed consent} - \text{onset date of AD}) / 365.25$ and displayed to 1 decimal place.

For the calculation 01JAN will be imputed as only onset year of AD is recorded. Duration of AD and severity of disease will be summarized using summary statistics for continuous variables.

Duration of AD and severity of insomnia will be summarized using the full analysis set.

Optional ApoE4 genotyping will be summarized using the full analysis set. Subjects will be classified as ApoE4 carriers if they will have one or more copies of the ApoE4 allele. That is, subjects of the genotypes e4/e4, e4/e3 and e4/e2. Subjects without the ApoE e4 allele will be classified as Non-carriers (i.e., e3/e3, e3/e2, and e2/e2). This definition will be used for the subgroup exploratory analysis ([Section 8.3.11](#)).

Severity of insomnia will be determined using a score cutoff of ≥ 5 in PSQI global score for insomnia at baseline. This definition will be used for the subgroup analysis ([Section 8.3.12](#)).

Alzheimer disease medications at baseline will be summarized using the full analysis set. Subjects will be classified as naïve if they do not take acetylcholinesterase inhibitors and/or memantine at baseline. This definition will be used for the subgroup exploratory analysis ([Section 8.3.13](#)).

This will be summarized post data base lock (DBL) once the data is analyzed.

All data will be listed on the safety analysis set.

